6. SPECIFIC AIMS

Aim 1: Develop an initial treatment manual for NEXT.

Aim 2: Iteratively pilot NEXT on two cohorts of participants, and collect qualitative feedback which will be integrated into the NEXT program. (Study 1)

Aim 3: Determine feasibility and acceptability of NEXT (Study 1 & 2)

Exploratory Aim: Evaluate Mediators and Moderators of NEXT (e.g, depression, eating behaviors, self-efficacy)

Aim 4: Establish preliminary effects of NEXT on weight loss, executive function, and self-monitoring through a randomized-control trial comparing NEXT + behavioral weight loss (BWL) to BWL alone (Study 2)

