Cognitive training, which targets aspects of EF, has improved cognitive performance and functional outcomes in healthy individuals and various populations with cognitive impairments. ¹⁸⁻²¹ Cognitive training has improved delay discounting among individuals with substance use disorders, ²² and inhibition and attention training paradigms in the context of high calorie foods have been associated with reduced palatable food consumption, reduced binge eating, and increased weight loss. ^{23,24} Cognitive Symptom Management and Rehabilitation Therapy (CogSMART) is a manualized compensatory cognitive training intervention targeting EF which is efficacious among individuals with traumatic brain injury. ^{25,26} A similar intervention is efficacious with individuals with psychosis. ²⁷ Modifying and applying CogSMART to address EF deficits found in people with overweight or obesity could improve weight loss and maintenance outcomes.

Computer training programs targeting implicit neurocognitive processes (i.e., attention, inhibition) show preliminary effects to change eating behavior and weight. ^{23,24} A number of experimental studies have demonstrated training inhibition can impact eating behavior and weight loss. ²⁴ Thus, it is promising that changing elements of EF can improve treatment outcomes.

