8. PROGRESS REPORT

Study 1 treatment materials were developed and recruitment of participants began in May 2019. The first group of 10 participants began baseline assessments in June 2019 and started in a 12-week pilot group in July 2019. The group program ended in October 2019 and 8 of 10 participants completed their post-treatment assessments thereafter. Some revisions were made to treatment materials based on feedback received from participants. Recruitment for the second pilot group began in September 2019 and participants completed baseline assessment visits thereafter. The second pilot group began group sessions in November 2019 and finished in February 2020 and 8 of 11 participants completed their post-treatment assessments.

Study 2 recruitment began in February 2020.

[name], the PI, has closely monitored the study. Recruitment has progressed according to plan for Study 1. There have been no formal reports given that no adverse events have occurred and all monitoring has been conducted by the PI and other internal team members.

Study 2 recruitment was recently completed.

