Assessment measures are specified below but assessments will occur at two additional time points for a total of four assessments per participant: baseline, at mid-program (take place approximately between sessions 10-14), post program, and 6 month follow-up. Assessment visits will be held in-person or in password-protected ZOOM meetings. Links for assessment tasks that can be completed online including computer tasks and surveys will be emailed to the participant before the assessment appointment with instructions on how to access the ZOOM meeting.

Table 1. Measurement table and assessment time-points for study 2:

	Instrument	Baseline	During group visits	Mid- program	Post- Program	6-month f- up
Anthropometry	Height/Weight	Х	Х	Х	Х	Х
	WRAT-4	Х				
Screening Measures	MINI	Х			Х	x
	Medical and medications	X		Х	Х	Х
Binge Eating	EDE	Х		Х	Х	Х
	EDEQ	Х	Х	Х	Х	X
	DKEFS	X		Х	Х	X
Executive Function	BRIEF	Х			Х	X
	PSI	Х		Х	Х	X
	Delay Discounting	X		X	X	Х
	Brain Health Index	X		Х	Х	X
	DFLEX	Х	X	Х	Х	х
	Digit Span	X		Χ	Х	Х
	WCST	X		Х	Χ	×
	CVLT- Food	X	X	X	Χ	×
	Stop Signal Task	X	X	Χ	X	X
	Tower of London	X	X	Χ	X	Х
	ТМТ	X	X	Х	Х	х
	СРТ	Х		Х	Х	Х
	PHQ-9	Х		X	X	х
	DERS	Х		Х	Х	х
Questionnaires psychiatric	GAD-7	X		Х	Х	х
Questionnaires stress	PSS	Х		Х	Х	×
Questionnaires eating behavior	YFAS 2.0	Х		Х	Х	х
	EAH	X		X	X	X
	Adult Eating Behavior Questionnaire (AEBQ)	Х		Х	Х	Х

	Reward Based Eating Drive Scale (RED)	Х		х	Х	Х
Questionnaires impulsivity	S-UPPS-P	Х	Х	Х	X	X
Questionnaires-self-efficacy	General Self Efficacy Scale	Х	Х	Х	Х	Х
Questionnaires other health behaviors	GPAQ	Х		Х	Х	Х
	Godin leisure time exercise questionnaire	X	X	X	X	X
	Q-LES-Q-SF	Х	Х	Х	Х	X
Adherence	ADH	Х		Х	Х	X
	BWL	X		X	X	×
Feasibility/Acceptability	Attendance		Х	Х	Х	Х
	Acceptability survey		X	X	X	×
Self-Monitoring	Habit books		Х			

Measurements

Screening Measures (baseline only): Participants will complete the Mini-International Neuropsychiatric Interview (MINI)²⁹ to confirm eligibility (i.e., absence of exclusionary psychiatric condition). The WRAT³⁰ reading assessment will be administered at baseline to evaluate reading level and ensure valid administration of the assessments.

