Anthropometry (all assessment timepoints and each program visit): At CHEAR Height will be measured using a portable Schorr height board (Schorr Inc, Olney, MD) in triplicate. Height will be recorded to the nearest 0.1 cm. Body weight in kilograms will be measured in triplicate on a Tanita Digital Scale (model WB-110A). Body weight will be recorded to the nearest 0.1 kg. The average of the 3 height and weight values will be used for analysis. Height and weight will be converted to body mass index (BMI=[kg/m²]). If height and/or weight is not collected at CHEAR, participants will be asked to self-report their height and weight using a scale they own or a Bluetooth provided scale.

Binge Eating (all assessment timepoints): The Eating Disorder Examination³¹ (EDE) interview will be administered as the EDE is the gold standard for assessing binge eating is a valid and reliable measure.

Executive Function (all assessment timepoints): Standardized, well-validated neurocognitive tests to assess a broad range of EF domains will be conducted. We will include selected subtests from the widely used Delis-Kaplan Executive Function System (D-KEFS)³² and various other well-validated measures of EF. Lastly, self-report measures of EF are included. Administration of all EF tasks should take about 80 minutes.

BRIEF: To identify individuals with EF difficulties, the Behavior Rating Inventory of Executive Function – Adult³³ (BRIEF-A) will be administered at baseline and again at post-program.

D-KEFS. ³² The D-KEFS is a widely used battery of EF that has strong validity and comparable reliability to other neuropsychological tasks. Three D-KEFS subtests (Color-Word Interference [CWI], Design Fluency, and

Verbal Fluency) will be administered.

Problem Solving Inventory (PSI).³⁴ Participants rate statements describing their own problem-solving behaviors and attitudes using 32, six-point Likert-type items. Three factors are derived: Problem Solving Confidence (self-assurance while engaged in problem solving), Approach-Avoidance Style (tendency to approach or avoid different types of problem-solving activities), and Personal Control (control over emotions and behavior while problem solving). The PSI has strong validity and reliability.³⁵

Delay Discounting³⁵ – Participants choose between two hypothetical rewards, one sooner and one more in the future to measure decision making.

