Data Analysis and Interpretation: The pilot aspect of this study is to help evaluate the feasibility and acceptability of the program to aid in program development for a future randomized control trial. Data analyses will consist primarily of descriptive data, evaluating weight loss change and changes in executive function by evaluating pre and post assessment changes. Qualitative data will be used to continue to improve the NEXT

program development. Women and minorities will be included in recruitment for this study. Typically previous weight loss studies have had \sim 75% women participants.

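### The only stated weight analysis is pre-to-post change; no stated analysis for the Study 2 randomised comparison uses the session, mid-program or 6-month weights or covers people without a post-program weight

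*Combined protocol and SAP*

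**What the plan says.** The only analysis text is the Data Analysis and Interpretation paragraph of section 9. It states that "Data analyses will consist primarily of descriptive data", carried out by "evaluating weight loss change and changes in executive function by evaluating pre and post assessment changes". It is introduced as concerning the pilot part of the work, whose purpose is "to aid in program development for a future randomized control trial".

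Aim 4 (section 6) asks more of Study 2: "Establish preliminary effects of NEXT on weight loss, executive function, and self-monitoring through a randomized-control trial", with NEXT plus BWL compared against BWL alone. For that comparison the document gives no between-arm model, time point, analysis population or missing-data rule.

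Data collection is much richer than two weights. The measurement text in section 9 is headed "Anthropometry (all assessment timepoints and each program visit". Study 2 has 20 sessions and assessments at baseline, mid-program, "post program, and 6 month follow-up". Weights not taken at the site may be self-reported. Section 20 offers Study 2 participants who withdraw a $25 gift card at each remaining assessment point if they choose to provide a weight. No such offer is described for Study 1.

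Section 8 reports that 8 of 10 participants in the first Study 1 cohort completed the post assessment, and in the second "8 of 11 participants completed their post-treatment assessments". Section 7 argues that an adapted cognitive training program "could improve weight loss and maintenance outcomes".

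**The concern.** A pre-to-post change score exists only for people who have the post weight. Someone who attends many sessions and then leaves contributes nothing, although the weights up to departure are on file. In a weight-loss program it is plausible, though the documents do not say so, that people who are losing little are more likely to leave. The mean among those who return would then be too favourable in Study 1 and in each arm of Study 2. If the arms also lose different numbers of people, part of the apparent arm difference would reflect who stayed.

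The 6-month weight is the only measurement after the program has ended, and it has no stated use.

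**Working it through.** **1. Weights collected against weights used.** Study 2: 20 sessions + 4 assessments = up to 24 weights per person. A pre/post change uses 2.

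**2. Missing post assessments in Study 1** (section 8). (10 − 8) + (11 − 8) = 5 of 21 = 23.8%. The Wilson 95% interval has centre (0.2381 + 3.8416/42)/(1 + 3.8416/21) = 0.279 and half-width 1.96 × √(0.2381 × 0.7619/21 + 3.8416/(4 × 21²))/1.183 = 0.172, which gives 10.6% to 45.1%.

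**3. Bias in a single mean.** Let m be the mean loss in everyone, L the mean loss the leavers would have shown, g = m − L, and d the share missing. The completer mean is (m − dL)/(1 − d), so the bias is g × d/(1 − d). At d = 5/21 the multiplier is 5/16 = 0.3125. The documents give no SD or expected loss, so m = 6.0 kg is an assumption.

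| Assumed mean loss in leavers | g | Bias (0.3125 × g) |
|---|---|---|
| 4.1 kg | 1.9 kg | 0.6 kg |
| 2.8 kg | 3.2 kg | 1.0 kg |
| 1.2 kg | 4.8 kg | 1.5 kg |

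Simulation gives the same range. The assumed values were 32 per arm, weekly weights for 24 weeks, slope −0.25 kg/week (SD 0.22, so 24 × 0.25 = 6.0 kg), residual SD 0.7 kg, and a drop-out hazard that rises with poor observed loss. At 24% drop-out, completers showed 6.6 to 7.5 kg depending on the strength of the hazard.

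**4. Bias in the arm difference.** Take no true difference, and assume 15% and 32% missing with the same g in both arms.

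- No weights recovered: the multipliers are 0.15/0.85 = 0.176 and 0.32/0.68 = 0.471, a difference of 0.294. For g of 1.7 to 3.1 kg the false difference is 0.5 to 0.9 kg, favouring the arm with more drop-out. Simulations gave 0.46 to 0.95 kg.
- Half the weights recovered, regardless of loss: 7.5% and 16% remain missing. The multipliers are 0.075/0.925 = 0.081 and 0.16/0.84 = 0.190, a difference of 0.109. For the same g this is 0.19 to 0.34 kg. Two simulations gave 0.26 and 0.32 kg.
- Equal drop-out of 24%: the multipliers cancel. Simulated completer changes were −7.00 and −6.97 kg.

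A separate simulation in SD units (true arm difference 0.5 SD, one drop-out rule for both arms, about 23% missing) agrees. Completers overstated each arm's mean by 0.09 to 0.18 SD, but the arm difference came out at 0.476 to 0.482.

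**5. What the collected weights can repair.** In the first simulation, a mixed model on all weights returned 6.0 kg per arm, and a false difference of 0.02 kg instead of 0.72 kg. In another run, adding only the mid-program weight took the false difference from 0.89 to 0.00 kg.

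**6. Where the repair stops.** Those runs let each person's course continue unchanged after departure. Suppose instead that leavers return to baseline weight by post-program. At 15% and 32% drop-out the true losses are then about 5.6 and 5.0 kg, yet the model still reports 6.0 in both arms and misses a real difference of 0.57 kg. If loss simply halts, the truth is 5.8 and 5.4 kg, again reported as 6.0.

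**The case against.** The strongest reply is that the document never adopts a pre/post-only analysis for Study 2. The paragraph speaks of the pilot, looks ahead to a later trial and says its analyses are primarily, not solely, descriptive. Study 1 has just two assessment visits, so pre/post suits it. This stands. A reader might infer that the other weights will be discarded, or that drop-outs are to be excluded by design. The text supports only the narrower statement that those weights have no stated use and that no missing-data rule exists. The narrower statement is enough: if the paragraph covers Study 2, its weight analysis is pre/post change; if it does not, Aim 4 has none. The remedy is the same.

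Several further replies also stand:

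- Section 20 actively seeks weights after withdrawal. The offer is voluntary and says nothing about analysis, but it could remove much of the bias.
- The 24% is non-attendance at a roughly 3-hour Study 1 visit paid at $50. Study 2 pays $100 and $150 for the post-program and 6-month visits, so 24% is not an estimate of its missing weights.
- Nothing in the documents shows that poor losers leave or that drop-out differs between arms. A reader might infer that the Study 2 comparison will be biased; that needs both assumptions.
- The model's clean recovery follows from its drop-out assumption, and a completer analysis does not test that assumption.
- Maintenance is rationale, not a numbered aim. The plan cannot be faulted for leaving an aim unanswered, only for giving the 6-month weight no stated use.
- Session weights may mix site and home scales, and treatment is delivered in groups of 10 to 20. A model confined to person-level effects does not settle either matter.

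**Conclusion.** The concern holds in limited form. Pre-to-post change is the only weight analysis named. The Study 2 comparison has no stated analysis that uses the session, mid-program or 6-month weights, and a change score drops anyone whose post-program weight is not obtained.

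The likely harm is to the single-arm means: roughly 0.6 to 1.5 kg too much on a true 6 kg at 24% missing. This assumes that leavers would have lost about 1.9 to 4.8 kg less than the average participant. Bias in the arm difference also requires unequal drop-out: about 0.5 to 0.9 kg at an assumed 15% versus 32% with nothing recovered, and about 0.3 kg with half recovered. Every kilogram figure rests on assumed values.

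A reader might also expect a gain in precision. That is not dependable: the SD of the arm difference was 1.35 against 1.48 kg in one simulation, but 1.38 against 1.41 kg in another. The case rests on less bias. It is a change the sponsor should make, not a flaw that invalidates the trial.

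**What to change.** Add a short Study 2 weight analysis to section 9:

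- Compare arms as randomised with a likelihood-based longitudinal model (arm, time, arm-by-time) of the baseline, mid-program, post-program and 6-month weights. Include weights given after withdrawal, and add session weights as further information on the course before drop-out.
- Report the arm difference at post-program and, as a secondary contrast, at 6 months, both in all randomised participants.
- Flag self-reported weights and repeat the analysis without them.
- Beside the model result, show the completer result and a sensitivity analysis in which missing weights return toward baseline.

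For Study 1, keep pre/post change and report with it an estimate that uses session weights where available.

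The cost is a paragraph of text and modest analyst time, with no new data. The downside is that the main model assumes drop-out depends only on weights already observed, which is why the return-to-baseline analysis is needed. Section 8 says Study 2 recruitment is complete, so the text should be fixed and dated before weights are examined by arm.

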10. HUMAN SUBJECTS

Study 1: It is expected that up to 60 individuals may be consented with a goal to have at least 20 participants enroll in pilot program who meet the following eligibility criteria for study 1, Inclusion criteria:

- 1. Age 18-65
- 2. Ability to read English at a 6th grade level
- 3. BMI >25 and <45
- 4. Difficulties with executive functioning

Exclusion Criteria:

- 1) Medical condition that requires physician monitoring to participate in weight control program or prohibits safely participating in recommended physical activity
- 2) Psychiatric condition that could interfere with program participant (e.g., substance abuse, suicide attempt within previous 6 months, active purging)
- 3) Currently pregnant, lactating or plan to be in the timespan of program follow-up
- 4) Current enrollment in an organized weight control program
- 5) Change in psychotropic medication or other medication that could have impact on weight during the previous 3 months
- 6) History of bariatric surgery
- 7) History of learning disorder, neurological condition or injury

Study 2: It is expected that up to 150 participants may be consented with the goal to have at least 64 participants randomized to start group in study 2 with the same eligibility criteria that was used in Study 1 (presented above).

11. RECRUITMENT AND PROCEDURES PREPARATORY TO RESEARCH

Participants will be recruited using online advertisements such as Craigslist, university listservs, flyers to physicians, flyers posting on campus, in the community, and in physician offices, and direct mailings and direct email to participants, radio ads, ResearchMatch, social media, and professional referrals to the lab from local physicians. Participants may be recruited through the use of electronic medical records (EPIC system), a request for partial HIPAA waiver for recruitment purposes is submitted to do so.

We will also recruit potential participants through a "snowball recruitment" effort. Participants who have completed the study and have indicated that they have agreed to be contacted about future research will be sent an email requesting them to refer potentially eligible families to our recruitment team to be screened for the project. Participants who are currently enrolled will also be emailed the same materials. The emails sent to participants will contain information about the programs currently recruiting participants, a link to our lab's website, and a previously approved recruitment flyer.

Participants who respond to recruitment efforts will be asked to complete an initial online screen to determine initial eligibility if individuals do not have online access, they can complete an extended screening call that will include these questions as part of the telephone screen. Participants who meet study inclusion criteria will then complete a phone screen to further assess eligibility. If participants meet initial screening criteria, following the phone screen, they will be scheduled for an orientation at an in-person meeting or in a password-protected ZOOM meeting to learn more about the study, review the informed consent and have all questions answered.

12. INFORMED CONSENT

The online screening will assess for basic inclusion and exclusionary criteria. This process presents no more than minimal risk of harm to subjects, the waiver will not adversely affect the rights and welfare of the subjects and the research could not practicably be carried out without the waiver. For these reasons, we request a waiver of documented consent for the online screening. For individuals who do not have online access, the questions asked on the online screen can be administered over the phone in conjunction with the phone screen. The phone screening will assess for basic inclusion and exclusionary criteria. Again, this process presents no more than minimal risk of harm to participants, the waiver will not adversely affect the rights and welfare of the subjects and the research could not practicably be carried out without the waiver. For these reasons, we request a waiver of documented consent for the phone screen.

All participants will complete written informed consent prior to enrollment at an orientation session. It is not likely that participants for this population will lack the capacity needed for consent. If there are any concerns, to ensure participants understand the consent form, they will be asked to describe what the study is about. For participants in which capacity for consent is judged to be questionable, they will complete the Mini-mental State Examination (MMSE) and if they receive under a 24, they will not be eligible for enrollment (i.e., surrogate consent will not be acceptable). It is highly unlikely that the MMSE will need to be administered to this patient population but if it is administered, documentation of the test results will be kept in the participant file.

This study will consent participants, either in-person or in a password-protected ZOOM meeting. For those who are consented in a ZOOM meeting, the participant will be emailed a copy of the consent form. During the ZOOM call, the study staff member will provide an opportunity for the potential participant to ask questions. When all of the potential participant's questions have been answered, the study staff member will ask the participant if they are ready to provide consent and then verbal consent will be obtained. Should the potential participant desire more time to make a decision to participate, they will be provided information on how to reschedule their ZOOM verbal consent call. We require a waiver of written consent for participants consented via zoom. Justification for this oral consent procedure is that the research presents no more than minimal risk of harm to subjects and involves no procedures for which written consent is normally required outside of the research context. If the participant consents, they will then be scheduled for the initial assessment to confirm eligibility.

Both remote and in-person orientation and consent processes may take place with a group of potential participants. Participants may ask questions as a group and they will also be informed that they can each have an opportunity to privately ask additional questions. For those who attend a group ZOOM orientation, the consent form will be explained to the group of potential participants and then the consent process will occur individually between one staff member and one potential participant using the breakout room function on ZOOM. The potential participant will be given the opportunity to ask questions privately and provide verbal consent privately. If individuals are unsure as to whether they are willing to participate in the study, they may take the consent form home with them. If they later decide they wish to participate, they may schedule their first assessment and sign the consent form or provide verbal assent prior to participating in the assessment.

CHEAR staff members able to provide information about the study and carry out the consent procedures include:

[name], [name], [name], [name] [name], [name], [name], , [name], [name], [name], [name], [name], [name], [name].

Partial waiver of HIPAA authorization is being requested to aid in the recruitment purposes. We are requesting this so participants can provide verbal confirmation to their physician about their interest in participating and the physician can provide us the participant's name, age/date of birth, and contact information. This use of disclosure

involves no more than minimal risk, granting this waiver will not adversely affect privacy rights and welfare of the individuals whose records will be used, this recruitment could not practicably be conducted without the waiver, this could not practicably be conducted with the PHI to know who to contact, identifiers will only be used for the stated purpose and will be kept securely in our facility and electronically protected. Identifiers will be destroyed as soon as possible and at a maximum 3 years after study completion. PHI will not be used for any other purposes. Participants will be provided with all pertinent information as soon as possible upon formal consent.

